4.2 Exclusion Criteria

Exclusion criteria include:

- Cognitive or psychiatric impairments that prohibit being able to provide informed consent.
- Any physical conditions that prohibit activity such as gentle yoga.
- Based on our experience with this population, we anticipate that most women will have access to a computer or mobile phone to access the digital support features of the intervention. For those without such access, we will provide a device and data plan to support participation.

4.3 Study Enrollment Procedures

Recruitment will occur by way of flyers placed in well-trafficked areas, information sheets provided to potential participants, and clinician referral at partner practices. Women who express interest will be contacted by a study staff member to arrange for a virtual meeting (by phone or video) to obtain consent and complete the baseline assessment, if eligible. Consented participants will then be randomized, by the lead project coordinator using a standard randomization process, in equal proportions to receive the intervention (MMORE) or treatment as usual condition. The lead project coordinator will meet virtually with participants to explain the study procedures and provide instructions to the digital support features (Intervention Only).

5. STUDY INTERVENTIONS

5.1 Interventions, Administration, and Duration

Mindful Moms: Yoga Mindfulness Intervention. The significant restrictions to in-person delivery of services at practice partner settings and continued institutional barriers to in-person research at partner settings due to the ongoing Covid pandemic have necessitated the need for alternative safe intervention delivery strategies for the Mindful Moms intervention. After consultation with our partner practice stakeholders and women with lived experience from our study advisory committee, we are modifying the intervention delivery mode to include virtual delivery of the intervention. We will deliver the group intervention virtually through a secured

Dartmouth-based video conferencing software (Zoom). The virtual intervention protocol will be 8 sessions, approximately 60-minutes in duration, conducted over the course of 10 weeks. Lead Instructor [name], professionally trained and certified in prenatal and trauma-informed yoga, will implement the group protocol sessions at the designated location. Sessions will be attended by at least one study team member. Sessions will be video or audio recorded (participants de-identified) to allow for assessment of fidelity in delivery of protocol.

All intervention participants will be provided with a tablet and mobile hotspot if needed in order to be able to access the virtual intervention sessions. All intervention participants will complete a training with research study staff about how to use the videoconferencing software. All intervention participants will be provided with a unique password-protected access link to the online support materials, as well as detailed instructions for how to access the materials. A unique study code will allow us to monitor individual participant use of the support modules for analytic purposes.

We have developed a safety protocol (overseen by Drs. [name] and [name]) to ensure strict attention to safety for women participating in the yoga intervention. As with other gentle yoga protocols, the safety protocol will include specific directions by the Intervention Instructor that participants do not have to partake in any of the poses or activities that feel uncomfortable, and adjustments will be made as needed to minimize discomfort for those participants that would like such adjustments. Lead Instructor [name] has over six years of experience leading trauma-sensitive yoga protocols with pregnant incarcerated women, a vulnerable population similar to that for the proposed project.

The Lead Instructor will complete the Session Event Checklist after each intervention session to denote any adverse events (non-serious and serious) that take place during the intervention sessions. Participants will complete the Intervention Experience Form at the end of each session to document experience of any adverse events including physical experiences (e.g., shortness of breath, pain, increased or decreased infant movement, or other discomfort experiences during the session) and psychological experiences (e.g., emotional flooding, uncontrollable crying). At the end of each intervention week, all participants will also complete a Weekly Monitoring Form that will include items related to any additional experience of adverse physical or psychological events. The project coordinator will administer the Weekly Monitoring Form by telephone or e-mail.

In the event that a study participant lapses or relapses during the study period, cases will be handled on an individual basis, which may be largely determined by the procedures of the partner maternity care practice in terms of preference for ongoing care. A lapse/relapse will not necessarily lead to participant discontinuation in the study.

Treatment as Usual. Treatment as usual is operationalized as the integrated medication assisted treatment being provided at the partner practice as part of the New Hampshire State Targeted Response 21st Century Cures initiative. Such treatment includes medication for opioid use disorder, individual and/or group counseling, and case management.

5.2 Handling of Study Interventions

All study yoga instructors will be trained on the use intervention protocol and will deliver the

protocol according to the procedures outlined in the Mindful Moms Intervention Manual. The manual outlines the theme and activities of a given session, as well as the content of the companion digital components aligned with the session.

5.3 Concomitant Interventions

5.3.1 Allowed Interventions

All consented participants will also be receiving treatment as usual at partner practices, which includes medication for opioid use disorder as well as individual and/or group counseling and case management.

5.3.2 Required Interventions

All participants will be receiving medication for opioid use disorder as part of integrated prenatal care at partner maternity care practices.

5.3.3 Prohibited Interventions

There are no prohibited interventions for this study. To account for contamination that may impact outcomes, the study team will document any other research or quality improvement initiatives that may be taking place at the partner practice that could impact study outcomes.

5.4 Adherence Assessment

Tracking intervention session attendance. The study lead project coordinator and the yoga instructor will track participant attendance at intervention sessions. The lead project coordinator will sign in each participant to the virtual intervention sessions using their unique study identification number.

Tracking use of digital features. Technology usage tracking features are incorporated in the digital website to monitor frequency of usage and features most accessed.

Tracking of TAU adherence. Participant adherence to TAU adherence (medication and group/individual counseling) will be evaluated at the end of the study intervention period through self-report and clinical record review.

Monitoring fidelity. Intervention sessions will be video recorded (with participants de-identified) to allow for assessment of fidelity and inter-teacher consistency in delivery of the intervention protocol. Fidelity will be assessed monthly by a team of coders led by the lead project coordinator, all having been trained to identify key content- and style-related components of the yoga-mindfulness intervention, using an appropriately adapted version of the Mindfulness-Based Relapse Prevention Adherence and Competence Scale (MBRP-AC), developed in consultation with MBRP scientist and project consultant [name]. Adherence to intervention protocol will also be documented by progress notes taken by study staff who attended the session.

6. STUDY PROCEDURES

6.1 Schedule of Evaluations

Assessment	BL	Intervention	Post	3M PP	Final Evaluation
Eligibility: Consent/Enrollment	X				
Demographics	X				
Current physical conditions that could be considered	x				
AE					
Opioid Abstinence	X		X	X	
MOUD Treatment Retention	X		X	X	
Depression	X		X	X	
Anxiety	X		X	X	
Stress	X		X	X	
Mindfulness	X		X	X	
Pain Perception	X		X	X	
Quality of life	X		X	X	
Substance use (past 3 months, past 30 days)	X		X	X	
Weekly Assessments (craving, mood, stress, mindfulness)		X			
Adverse Events		X	X	X	
Experiences of Care (qualitative)				X	
Fidelity, Acceptability, Reach, Feasibility, Sustainability (Practice Level)					X
Organization Readiness for Implementing Change (Practice Level)		X			X
Program Sustainability (Practice Level)					X

6.2 Description of Evaluations

Outcomes. Participant outcomes will be assessed by way of clinical record review of consented participants and participant self-report. Implementation outcomes will be assessed through intervention usage data, and quantitative and qualitative methods.

Clinical Record Data Collection Procedures: The trained lead project coordinator will conduct chart reviews using approved data collection procedures the research team has used in other studies with this target population. Chart reviews will be conducted at intervals corresponding to 3 months postpartum for participants.

As used in other approved studies conducted by the study team, the research team will work with each practice partner to identify the best strategy for conducting chart review for consented study participants. The practice will provide the identified record list and the lead project coordinator will create a master-code that includes only the respective record numbers and unique study IDs. The master-code will be stored in separate, secured location at the respective partner practice and will only be referred to by the research team for the purposes data quality to ensure completeness of the research database.

The lead project coordinator will collect the chart data using a REDCap Clinical Data Collection template that includes only the corresponding unique study ID. All chart review data collection will occur at the partner practice location and the de-identified research data will be stored on the secured, HIPAA-compliant Dartmouth College REDCap server.

The master-code will be the only linkage between the unique study identifiers contained in the database and the patient record identifier. Upon completion of all data collection and analyses, the master-code will be destroyed so there will be no link to identifiable records in the study. We will not collect any individual identifiers as part of the research database. The single source of PHI (MRN) will be associated only with the unique study ID in the master-code. The PHI will be accessible only to the principal investigator and authorized study staff. The PHI will not be disclosed to any other person or entity.

Clinical Record Data Indicators. The following assessment metrics will be collected from clinical records of consented participants:

Primary End Points:

MOUD Treatment Retention. Treatment retention will be operationalized as a composite of medication adherence (number of weeks buprenorphine or methadone present in the urine toxicology report) and treatment adherence (number of weeks attended required counseling as part of comprehensive treatment as usual, as indicated in clinical notes) - throughout the prenatal period to 3 months postpartum.

Opioid use abstinence. Weekly point of care urine toxicology screening is conducted as part of standard care with all MOUD patients at partner practices to assess for THC, cocaine, benzodiazepines, methamphetamine, opioids, methadone and buprenorphine. Opioid abstinence will be measured as number of weeks consistently abstinent from opioids over the perinatal period to 3 months postpartum.

Secondary End Points:

Other substance use. Other substance use will be measured as number of weeks the participant used marijuana and/or other drugs as indicated in urine toxicology reports. Tobacco and alcohol use will be measured by way of documentation in clinical notes from visits.

Participant Self-Report Procedures: Participants will complete secured online survey assessments at baseline, post-intervention, and 3-months postpartum. The project coordinator will ensure that participants receive the assessment surveys at the specified times in the manner preferred by the participant. If participants wish to receive the survey via email, the survey will be sent as a unique study-identified password-protected link. The project coordinator will monitor and track survey assessment completion and ensure that participants receive gift card incentives for survey completion in a timely manner. For participants who do not wish to complete the survey online, the project coordinator will arrange for either a phone interview with the participant to complete the survey or will mail the participant the survey along with a self-addressed and stamped envelope for the participant to return the survey. The assessment survey will include the following:

Primary End Points:

Treatment Retention. Self-reported adherence to medication for opioid use disorder will be assessed by an adaptation of items from the well-established Adherence to Medication questionnaire originally developed for assessing adherence to antiviral medications among persons with HIV/AIDS. (i.e., when was the last time you skipped buprenorphine medication? [past 2 days, within the past 2 weeks, 2-4 weeks ago, 1-3 months ago, never skipped past 3 months]. Participants will also report how often they attended group/individual counseling in the past 3 months [every week, every other week, once a month, less than once a month].

Opioid abstinence. The reliability of self-report of substance use for pregnant and parenting women is especially complicated due to well-founded fears of child protective service involvement and potential loss of children. That said, when research studies are well-conducted and assurances for protection of participant privacy are clear and conveyed with messaging informed by community partners with lived experience, women do reliably self-report their use behaviors.

Opioid use will be assessed with relevant items from the Alcohol, Smoking and Substance Involvement Screening Test, aligned with relevant timeframes (baseline: past 6 months, post-intervention and 3 month postpartum: past 3 months). Opioid use disorder severity will be assessed with items corresponding to DSM-V diagnostic criteria.

Secondary End Points:

Other substance use:

Self-reported frequency and quantity of opioid and other substance use (including alcohol, marijuana, and tobacco) will be assessed with the Alcohol, Smoking and Substance Involvement Screening Test, aligned with relevant timeframes (baseline: past 6 months, post-intervention, 3 month postpartum: since last survey).

Mental Health:

Depression will be assessed using the Edinburgh Prenatal and Postnatal Depression Scales, both of which have been used extensively with the target population.

Anxiety will be assessed with the Generalized Anxiety Disorder Scale (GAD-7)², a psychometrically sound instrument routinely used in general health care settings.

Stress will be assessed with the Perceived Stress Scale,³ a psychometrically sound instrument that has been used in other studies of contemplative interventions with pregnant women⁴⁻⁷.

Posttraumatic stress will be assessed with the abbreviated PTSD Checklist (PCL-5), a screening instrument developed for primary care and other general medical settings, and used in studies with the target population.⁸

Mindfulness. Mindfulness will be assessed with the Mindful Attention Awareness Scale. This instrument has been used with demonstrated good psychometrics in mindfulness intervention studies with pregnant women and substance-using populations⁹⁻¹².

Quality of Life. Quality of life will be assessed with the World Health Organization QoL BRF, a widely used instrument with demonstrated validity and reliability with pregnant and early postpartum women.

Pain Perception. Pain Perception will be assessed by a widely used visual analog scale (VAS) used in other studies with pregnant women. Participants report point areas and levels of pain on a scale from 0 (no pain) to 10 (worst possible pain) and anchored with descriptive faces.

Implementation Outcomes. Endpoints for this non-powered exploratory aim include: 1) Intervention Acceptability, 2) Feasibility, 3) Fidelity, 4) Reach, and 5) potential Sustainability within practice infrastructure.

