6.2.3 Blinding

The study will be blind to the Principal Investigator, the statistician, and to those on the team responsible for participant data collection. We will work to try to blind clinicians delivering TAU to participant assignment but there is a chance that patients will reveal their condition to clinicians despite our best efforts. To achieve blindness, treatment assignment will be done by the lead project coordinator, who will not be directly involved in evaluation or data collection. Survey data collection will be conducted by the project coordinator who will be blinded to participant treatment assignment. Participant self-report surveys will be implemented using secured online survey software, which will significantly limit the potential of the project coordinator to introduce bias.

Stakeholder	Blind Status	Involved in Data Collection?	Steps to ensure blindness
TAU Clinicians	Potentially un-blinded	No	Patient participants may indicate to their clinician that participating in study. Clinicians will be instructed not to specifically ask patients about study.
PI	Blinded	No	The PI will not be involved in the group assignment or collection of data; analyses will be conducted when data are unlocked.
Statistician	Blinded	No • Will conduct analyses	Will not have access to randomization algorithm key
Project Coordinator	Blinded, with possibility of being inadvertently un-blinded	Yes	
 Will be instructed not to inquire with participants about study. Will report instances of learning status Assessments conducted via secured online survey software.
Lead project coordinator	Un-blinded • Knows random assignment • Introduces participants to their treatment condition	No	

	
 • Prepares necessary reports 		
--	--	--	--

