10. DATA COLLECTION AND QUALITY ASSURANCE

10.1 Data Collection Forms

Opioid abstinence and MOUD treatment retention will be collected by way of medical chart data extraction and self-report by consented participants.

Secondary outcomes will be collected by way of self-report by consented participants through completion of assessment surveys.

Case Report data collection forms have been created for the following:

- Participant Demographics and physical conditions at baseline
- Session Events Form
- Intervention Experience Form
- Weekly Monitoring Form
- Adverse Events
- Clinical Record Data Collection Template
- Self-Report Assessment Battery (SRAB)

The SRAB has been programmed in secured, password protected HIPAA compliant online survey software (Dartmouth College REDCap). Individual participant survey links will correspond to the unique participant study ID so that all pages of each assessment survey (and corresponding database) will be linked to the participant.

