10.3.3 Metrics

Intervention sessions will be video and audio recorded to allow for evaluation of fidelity over the

course of the study.

The study team will review data weekly to ensure quality and completeness.

The study data engineer will develop and maintain the database and prepare the dataset for analyses.

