10.3.5 Monitoring

Data accuracy and completeness will be monitored by the lead project coordinator.

The Independent Monitors will also receive quarterly summaries of study progress, recruitment and retention indices, and any adverse events.

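### The un-blinded lead project coordinator abstracts the chart data for both primary endpoints (6.2), although 6.2.3 places that role outside evaluation and data collection

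*Combined protocol and SAP*

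**What the plan says.** Section 6.2 (Clinical Record Data Collection Procedures) gives the chart work to one role twice: "The trained lead project coordinator will conduct chart reviews using approved data collection procedures the research team has used in other studies", and "The lead project coordinator will collect the chart data using a REDCap Clinical Data Collection template". The indicators it then lists from those records include both primary endpoints. Retention combines weeks with medication present on toxicology and weeks of counselling attended according to clinical notes. Abstinence is a count of weeks, set out alongside weekly urine screening.

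Section 6.2.3 explains how blinding is to be achieved: "treatment assignment will be done by the lead project coordinator, who will not be directly involved in evaluation or data collection". Its table marks the lead project coordinator as un-blinded and answers No to involvement in data collection. The same section says that those responsible for participant data collection are blinded. The one blinded collector it names handles surveys: "Survey data collection will be conducted by the project coordinator who will be blinded to participant treatment assignment".

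Three other places bear on the point. Section 5.4: "The lead project coordinator will sign in each participant to the virtual intervention sessions using their unique study identification number". Section 10.3.5: "Data accuracy and completeness will be monitored by the lead project coordinator". Section 10.1: "Opioid abstinence and MOUD treatment retention will be collected by way of medical chart data extraction and self-report by consented participants".

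**The concern.** Section 6.2.3 relies on separating the person who assigns treatment from the people who collect outcomes. Section 6.2 removes that separation for the chart-based primary outcomes, and 10.3.5 gives the accuracy check to the same un-blinded role.

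Where the chart leaves room for judgement, an abstractor who knows the arm could, without intending to, code the arms differently. Such room exists when deciding from a clinical note whether a counselling week was attended, or when handling a week with no test or an unclear one. At stake is whether the trial can report its chart-based primary outcomes as collected blind, as the description of the trial as blinded in 9.1 would lead a reader to expect.

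**Working it through.** **1. The roles side by side**

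| Task or status | Role | Section |
|---|---|---|
| Randomizes participants | Lead project coordinator | 4.3, 6.2.2, 6.2.3 |
| Un-blinded; data collection: No | Lead project coordinator | 6.2.3 table |
| Conducts chart review, enters chart data, creates the master-code | Lead project coordinator | 6.2 |
| Monitors accuracy and completeness | Lead project coordinator | 10.3.5 |
| Administers the Weekly Monitoring Form | Project coordinator (5.1); lead project coordinator (7.1) | 5.1, 7.1 |
| Collects surveys, blinded | Project coordinator | 6.2.3 |

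**2. Do innocent readings remove the conflict?**

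- *Loose wording.* The 6.2.3 table has separate rows for the two coordinators, and 6.2 says lead each time.
- *Only indirect involvement.* Entering chart data into the collection template is direct data collection, and the table entry is unqualified.
- *The study ID masks the arm.* The template carries only the ID, but this role assigns treatment and signs MMORE participants in to sessions by that ID.
- *An independent check exists.* Section 10.3.3 says "The study team will review data weekly to ensure quality and completeness" but names nobody and does not mention blinding. No supplied section provides duplicate or masked abstraction.

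**3. How much could it matter? Illustration only**

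The documents give no miscoding rate, no direction and no SD for week counts, so the shifts below are assumptions.

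Input: 150 less 20% attrition (9.2) leaves 120, or 60 per arm.

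Check against the plan: for a two-sample t-test with df = 118 and two-sided 0.05, a difference of 0.52 SD has noncentrality 0.52 × √(60/2) = 2.848 and power 80.6%. Section 9.2 states 80%. This confirms only the 60 per arm, because that figure concerns weeks abstinent in the 8-week period, whereas 6.2 counts weeks to 3 months postpartum.

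*Week counts.* With no true effect, arm-dependent coding that shifts the mean by 0.05, 0.10 or 0.20 SD in either direction gives rejection rates of 5.8%, 8.4% or 19.2% instead of 5.0%.

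*Binary outcomes, one time-point contrast (9.6).* Let p1 be the true rate in both arms and f the fraction of MMORE failures recorded as successes. Then p2 = p1 + f(1 − p1), d = p2 − p1, se0 is the pooled and se1 the unpooled standard error, and the rejection rate is Φ((d − 1.96·se0)/se1) + Φ((−d − 1.96·se0)/se1).

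Example with p1 = 0.60 and f = 0.10: p2 = 0.64, d = 0.04, se0 = 0.0886, se1 = 0.0885, giving 7.3%. The three values of p1 are the TAU rates assumed in 9.2.

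| True rate | f = 5% | f = 10% | f = 20% |
|---|---|---|---|
| 60% (retention) | 5.6% | 7.3% | 14.9% |
| 70% (retention) | 5.4% | 6.5% | 11.4% |
| 80% (abstinence) | 5.2% | 5.9% | 8.8% |

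These figures apply only to outcomes taken from the chart.

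**The case against.** The strongest reply is that the practical exposure may be small. Recorded toxicology results leave little to judgement, and abstinence is described in terms of them. Both primary endpoints are also self-reported through a coordinator stated to be blinded, and the time points of the GEE in 9.6 (8 weeks and 3 months postpartum) fit the survey schedule as well as the chart. If self-report feeds the GEE, the binary table above does not apply.

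This stands as a limit on size. It does not remove the conflict. The plan never says which source governs, nor that one source checks the other. The t-test on weeks retained in 9.6 fits the chart definition in 6.2, because the self-report retention items give categories rather than week counts.

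A reader might infer more: that the primary results will be biased towards MMORE, that the type I error is in fact inflated by the amounts shown, or that blinding fails throughout the trial. The documents support none of these. They give no evidence of differential coding or of its direction, the figures follow from assumed miscoding, and survey collection is separately assigned to a blinded role. Nor can it be said that no safeguard exists anywhere: the detailed chart procedures, the REDCap template and the Data Safety and Monitoring Plan were not available for this review.

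**Conclusion.** The contradiction holds on the text alone and needs no assumption: one role holds the allocation and abstracts the chart data for both primary endpoints, while 6.2.3 declares it outside data collection. As written, the rule that data collectors are blinded fails for the chart-based outcomes.

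The consequence is bounded but not quantifiable. It concerns mainly counselling weeks and untested or ambiguous weeks, is small for recorded toxicology, and vanishes where blinded self-report is the analysed source. The illustrative figures should not set the severity. This is a point that should be fixed, and no more than that: it touches both primary endpoints and is cheap to correct, but no bias has been shown.

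**What to change.** 1. In 6.2 and 10.3.5, assign chart abstraction and its accuracy check to an existing team member without access to allocation. Keep allocation apart from the chart dataset until abstraction is locked.
2. The documents do not show that a blinded person who collects no surveys is available. If the abstractor is the survey project coordinator, do all chart abstraction for a participant after her 3-month postpartum survey. This must include the record review of adherence that 5.4 places at the end of the intervention period, which would then be extracted retrospectively for that window. Log any un-blinding through chart notes.
3. Reconcile 5.1 and 7.1 on who administers the Weekly Monitoring Form, and correct the No in the 6.2.3 table for any collection duty that the lead project coordinator keeps.
4. If reassignment is not feasible, have a blinded existing member re-abstract a sample of charts, counselling weeks first. At minimum, correct 6.2.3 and 9.1 to state that chart-based primary outcomes are not collected blind.

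The cost is a transfer of duties, short text edits and chart-access training. The downsides are later availability of the end-of-intervention adherence data and some risk that chart notes reveal the arm to the new abstractor. The minimum option in step 4 needs text edits only.
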